- 3. Severe other diseases which started before the "study pregnancy" and lasted into the "study pregnancy" period, including congenital heart disease, arrhythmia, history of myocardial infarction (MI), history of stroke, or active cancer
- 4. Serious physical injury that occurred during the "study pregnancy": severe car collision injury, serious injury at home/work, etc. Multiple gestation (i.e., pregnancy with more than one baby at a time, such as pregnancy with twins, triplets, and quadruplets) in the "study pregnancy"

Study Design and Recruitment

Study group: Study group participants will be recruited from Nerivio's user base. An invitation message will be sent via in-app notification and/or email to all Nerivio users who are (1) female, AND (2) between 18 and 42 years of age as of November 1st, 2019 - March 31st, 2021. Users who meet these criteria will be invited to fill in a screening and eligibility questionnaire. If they meet the eligibility criteria, they will be offered the opportunity to participate in the study. Participants will complete and sign an electronic informed consent form. Following consent, participants will be asked to complete the questionnaire. Once complete, participants will be compensated for their time.

Control group: Control group participants will be referred to the study by site co-investigators, who are US licensed healthcare providers seeing women with headache disorders and/or women during their pre-pregnancy and/or pregnancy period. Patients interested in participating will be directed to the same screening and eligibility questionnaire and will follow the same study design.

Endpoints

Endpoints focus on the health of the mother and the baby, during pregnancy and three months postpartum.

Primary endpoint:

Demonstrate that the study group is not different than the control group in regard to gestational age at delivery (measured in pregnancy weeks).

QMS document

TCH-011 Clinical Study Protocol

Doc ID: TECXXXX

Revision #: 1.0

Page: 6 of 25

Secondary endpoints:

Demonstrate that the study group is not different from the control group in:

- 1. Baby's birth weight (average birth weight)
- 2. Miscarriage rate (% of miscarriage cases)
- 3. Preterm birth rate (% cases of preterm pregnancies, as measured in % of pregnancy weeks less than 37)
- 4. Birth deficits rate (% of birth deficits)
- 5. Still births rate (% of still births)

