Appendix 1: Screening and Eligibility Procedure

Thank you for your interest in this study. We will be assessing the effect of having migraine and using Nerivio, an acute migraine treatment, on the health of mothers and babies during pregnancy and 3 months postpartum, in mothers who suffer from migraine.

To assess your eligibility for the study, please answer the following screening questions.

If you meet the eligibility criteria, you will be directed to an electronic informed consent form, followed by the study questionnaire.

Eligible participants who complete the study questionnaire will be compensated for their time, with a \$100 gift card.

The following questions refer to your latest, completed, pregnancy (if you are currently pregnant, do not refer to the current pregnancy when answering the following questions). We will refer to that pregnancy (i.e., the completed pregnancy) as the "study pregnancy".

Page break

- 1. Was your entire "study pregnancy" period (from conception to delivery) between November 1st, 2019, and March 31st, 2022?
 - Yes
 - No

No = not eligible

- 2. Were you between 18 and 42 years of age when your "study pregnancy" began (at the date of the last menstrual period, LMP)?
 - Yes
 - No

No = not eligible

- 3. Did the "study pregnancy" have more than one baby, such as pregnancy with twins, triplets, and quadruplets (i.e., multiple gestation pregnancy)
 - Yes
 - No

Yes = not eligible

4. Have you ever diagnosed with migraine by a licensed healthcare provider?

QMS document

TCH-011 Clinical Study Protocol

Doc ID: TECXXXX
Revision #: 1.0

Page: 9 of 25

	• Yes
	• No
	No = not eligible
5.	Were you diagnosed with migraine prior to your "study pregnancy"?
	• Yes
	• No
	No = not eligible
6.	Did you have migraine attacks during your "study pregnancy"?
	• Yes
	• No
	No = not eligible
7.	On average, did you have migraine at least 4 days a month, during the six months prior to the "study pregnancy"?
	• Yes
	• No
	No = not eligible
8.	Did you have at least 4 migraine attacks during your "study pregnancy"?

- a. Voc
 - Yes
 - No

No = not eligible

- 9. Did you suffer from congenital heart disease, arrhythmia, history of myocardial infarction (MI), history of stroke, or active cancer before/during the "study pregnancy"?
 - Yes
 - No

Multiple choice; If Yes = not eligible

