- 10. Were you seriously injured during your "study pregnancy", e.g., had a car accident, work injury, home accident, assault, etc.?
 - Yes

TCH-011 Clinical Study Protocol

Doc ID: TECXXXX

Revision #: 1.0

Page: 10 of 25

No

Yes = not eligible

- 11. Do you have a history of preterm birth (delivery at gestational age under 37 weeks) with any of your previous pregnancies (before the "study pregnancy")?
 - Yes
 - No

Yes = not eligible

- 12. Do you have a history of congenital malformations or birth defects in any of your previous pregnancies (before the "study pregnancy")?
 - Yes
 - No

Yes = not eligible

Eligibility messages:

Not eligible message: Message presented to subjects if they do **not meet** the eligibility criteria as identified during the screening questionnaire:

Thank you for your interest in the study on migraine treatments during pregnancy. However, the information you provided indicates that you do not meet the study eligibility requirements, and therefore cannot participate in this survey study.

Eligible message: Message presented to subjects upon the completion of the screening questionnaire, if they **meet** the eligibility criteria as identified during the screening questionnaire:

Thank you for your interest in the study on migraine treatments during pregnancy.

The information you provided indicates that you are eligible to participate in this survey study.

You will now be directed to an electronic informed consent form. Please read the consent form carefully. If you consent, please provide your details and electronic signature at the bottom of the consent form.

Once signed, you will be directed to the survey study questionnaire.

The questionnaire contains 52 questions. It should take approximately 30-40 min to complete the questionnaire.

In order to make it easier and faster to answer the survey questions, we recommend you prepare documents you received upon hospital discharge following delivery of your "study pregnancy", prior to answering the questionnaire.

Please select your referral clinic:

QMS document

TCH-011 Clinical Study Protocol

Doc ID: TECXXXX
Revision #: 1.0

Page: 11 of 25

- 1. Clinic A
- 2. Clinic B
- 3. Clinic C
- 4. Clinic D
- 5. Clinic E
- 6. Other

Single choice

Present the matching ICF, based on participant's clinic

QMS document

TCH-011 Clinical Study Protocol

Doc ID: TECXXXX

Revision #: 1.0

Page: 12 of 25

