TCH-011 Clinical Study Protocol

Doc ID: TECXXXX
Revision #: 1.0

Page: 16 of 25

PIO	locoi	

- Botox® injection for migraine prevention (Botulinum toxin)
- Aimovig[®] (Erenumab)
- Ajovy® (Fremanezumab)
- Emgality® (galcanezumab-gnlm)
- Vyepti® (eptinezumab-jjmr)
- Nurtec® ODT (Rimegepant)
- Devices (e.g., gammaCore, Cefaly)
- Other
- Did not use any preventive treatment

Check all that applies

- 12. Have you been diagnosed with migraine with aura by a licensed healthcare provider? (Aura is a neurologic symptom that occurs typically before or during migraine that lasts 5-60 minutes and is characterized by an evolution of neurologic symptoms such as flashing lights or colors that grow in your visual field)
 - Yes
 - No
- 13. Do you usually experience aura right before your headache attacks?
 - Always
 - Sometimes
 - Never
- 14. Have you ever used Nerivio® to treat your migraine attacks?
 - Yes
 - No
- 15. How many prior pregnancies before the "study pregnancy" have you had?

Choose from 0 to 10 and "more than 10"

16. How many of these were completed pregnancies?

QMS document

TCH-011 Clinical Study Protocol

Doc ID: TECXXXX

Revision #: 1.0

Page: 17 of 25

Show question if >0 in the previous question. Responses: Choose from 0 to 10 and "more than 10"

- 17. Is there a family history of congenital defects or malformations?
 - Yes
 - No

Part 2 – Study pregnancy

The following questions refer to you latest, completed, pregnancy, termed "study pregnancy" (if you are currently pregnant, please do not refer to this pregnancy when answering the questionnaire).

- 18. What was the first day of the last menstrual period (LMP) before your "study pregnancy"? (Please provide accurate month and year. If you do not recall the exact day within the month, please choose 1st day of the month).
 - Choose on calendar / enter date (month, year; day is optional)

Year and month are good enough. Day is optional.

- 19. What was the delivery date of your "study pregnancy"?
 - Choose on calendar
- 20. What was your baby's gestational age at delivery or at the end of pregnancy (pregnancy length measured by number of weeks and days) of your "study pregnancy"

Choose on "roller", allow weeks (6 to 42 weeks) and days (+0 to 6 days). If possible, allow weeks and days separately..

- 21. What is the status of your "study pregnancy"?
 - Live birth
 - Elective termination
 - Spontaneous abortion (or miscarriage)
 - Late fetal death

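### Survey question 16 leaves *completed* undefined, so for women with an earlier pregnancy parity cannot be reliably derived and previous miscarriage cannot be isolated

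*Combined protocol and SAP*

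**What the plan says.** In Appendix 2, Part 1, question 15 asks for the number of pregnancies before the study pregnancy. Question 16 then asks "How many of these were completed pregnancies", under the display rule "Show question if >0 in the previous question". The answer is a single count from 0 to more than 10, with no definition and no breakdown by outcome.

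Both forms use the same word in their introductions to separate a pregnancy that is over from a current one. Appendix 1 says "We will refer to that pregnancy (i.e., the completed pregnancy) as the" study pregnancy. Appendix 2, question 21, lets that pregnancy be a live birth, an elective termination, a late fetal death or "Spontaneous abortion (or miscarriage". Question 20 accepts a length of 6 to 42 weeks, at delivery or at the end of pregnancy.

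The only other direct questions about earlier pregnancies are the two screen-outs in Appendix 1: "Do you have a history of preterm birth (delivery at gestational age under 37 weeks) with any of your previous pregnancies" (question 11), and previous malformations or birth defects (question 12). Secondary endpoint 2 is "Miscarriage rate (% of miscarriage cases" by group. The Statistical Analysis Plan section lists exclusions from analysis and names no covariate or model for any endpoint.

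**The concern.** The comparison is not randomised. Device users come from the company's user base, and controls are referred by headache and obstetric providers. Parity and history of loss may therefore differ between the groups, and both are natural candidates for adjustment.

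The design also gives parity a role of its own. The exclusions for previous preterm birth and previous malformation can act only on women who have been pregnant before. Mothers with an earlier birth enter selected for good outcomes, while first-time mothers enter unselected. For miscarriage and stillbirth, the plan neither restricts on the woman's history nor records it by type.

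For the primary endpoint, the study is deemed successful if the null hypothesis is not rejected. Confounding that hides a difference would thus favour success. If history is not recorded in usable form, an adjustment added later has little to work with.

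**Working it through.** **1. The two readings of question 16.**

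- *Wide reading (pregnancy has ended).* This follows the introductions to both forms and questions 20 and 21. Every pregnancy before the study pregnancy has ended, so question 16 equals question 15 for every woman. The difference is 0 and no previous loss is detected.
- *Everyday reading (carried to delivery).* Screening question 1 (conception to delivery) and survey question 19 (delivery date) lean this way. Question 15 minus question 16 then counts miscarriages and elective terminations together. It stays unclear whether a stillbirth was counted as completed.

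If a share q of women uses the wide reading, the difference detects a previous miscarriage with sensitivity 1 − q: 100%, 75%, 50%, 25% and 0% for q = 0, 0.25, 0.50, 0.75 and 1. The documents do not give q, and no item shows which reading a woman used. Even at q = 0, a woman whose only loss was a termination looks the same as one with a miscarriage.

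**2. What can still be recovered.**

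- Question 15 = 0: no earlier birth and no earlier loss, under either reading.
- Question 15 > 0 with question 16 = 0: no earlier birth.
- Question 24, repeat cesarean: an earlier delivery, for that subset only.

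**3. The plan's own yardstick.** The plan gives no figure on this point. Its stated precision for gestational age, with SD 2.7 and 114 per group, reproduces: 1.96 × 2.7 × √(2/114) = 0.70 week. At the cap of 400 per group, 1.96 × 2.7 × √(2/400) = 0.37 week.

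**4. Size of the possible bias.** All inputs in this step are assumptions, because the documents give none.

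*Miscarriage.* Let previous loss be present in a share a = 0.20 of one group and b of the other, and multiply risk by RR. With no device effect, the observed ratio is [1 + b(RR − 1)] / [1 + a(RR − 1)].

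| b | RR 1.5 | RR 2 | RR 3 |
|---|---|---|---|
| 0.30 | 1.15/1.10 = 1.045 | 1.30/1.20 = 1.083 | 1.60/1.40 = 1.143 |
| 0.40 | 1.20/1.10 = 1.091 | 1.40/1.20 = 1.167 | 1.80/1.40 = 1.286 |

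*Gestational age.* Bias = imbalance in parity × effect of parity. For 10 to 30 points and 0.1 to 0.5 week, it runs from 0.10 × 0.1 = 0.01 to 0.30 × 0.5 = 0.15 week.

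*Preterm birth.* Assume a risk of 9–10% in first-time mothers and 4–6% in screened mothers with an earlier birth, a gap of 3 to 6 points. If the share of first-time mothers differs by 20 to 30 points, the shift runs from 0.20 × 3 = 0.6 to 0.30 × 6 = 1.8 points. The 95% half-width for a difference between groups is 1.96 × √(2p(1 − p)/n). For p = 5–10% this is 5.7–7.8 points at 114 per group and 3.0–4.2 at 400.

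*Stillbirth.* At an assumed rate of 0.5–1%, the expected number per group runs from 0.005 × 114 = 0.6 to 0.01 × 400 = 4 events.

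**The case against.** The strongest reply is that the wide reading makes question 16 pointless. Question 15 already limits the count to pregnancies that are over, so asking how many of these were completed presupposes a subset. Most women would probably take it to mean carried to delivery. That is plausible, and the documents give no rate of misreading. But the everyday reading still does not isolate previous miscarriage, and a woman who follows the form's own usage cannot be told apart afterwards.

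A reader might infer that parity and previous losses cannot be derived at all and that no later analysis could repair the comparisons. The documents do not support that. The recoverable groups in step 2 allow restriction or stratification on no earlier pregnancy, at a cost in sample size, and results could be bounded under both readings.

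A reader might also infer that question 16 blocks a planned adjustment. There is none to block, and the missing adjustment plan is the larger gap.

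Two further objections stand. A previous-stillbirth covariate could not be usefully estimated from so few events. And the miscarriage comparison has a separate selection problem: entry requires at least 4 attacks during the pregnancy, plus at least 3 device treatments in the study group only. Early losses are therefore filtered unequally, and adjustment for history does not cure that.

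**Conclusion.** The point holds in a limited form. *Completed* is undefined at question 16, the forms' own usage includes miscarriages, and no other item counts earlier births or losses by type. Among women with an earlier pregnancy, parity is unreliable and previous miscarriage is not separable.

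The consequence is greatest for miscarriage, where the assumed inputs give a spurious rate ratio of 1.05 to 1.29. The documents give no miscarriage rate, so that factor is not set against a confidence interval here. For gestational age the bias is probably small: at most 0.15 week against 0.70 at 114 per group, or 0.37 at 400. The preterm shift stays below the half-width throughout the assumed range. These sizes rest on the assumed imbalances and risks, not on trial data. The sample size of 114 per group is not affected.

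This is a cheap improvement to a non-randomised comparison; it does not make the primary analysis invalid.

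**What to change.** Replace question 16 with four counts, shown only if question 15 is above 0 and required to add up to it: previous live births, miscarriages, stillbirths or late fetal deaths, and elective terminations.

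In the analysis plan:

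- adjust or stratify gestational age, birth weight and preterm birth by first birth (yes/no);
- adjust or stratify miscarriage by previous miscarriage (yes/no) as a sensitivity analysis, stating that this does not address selection through the minimum-attack and minimum-treatment criteria;
- report previous stillbirth descriptively only.

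The survey change is one item reworded before launch. Its downside is a slightly longer and more sensitive question. Defining *completed* alone would be cheaper and would remove most of the ambiguity about parity, but it would still leave miscarriage pooled with other losses. The analysis-plan change is somewhat more than a line or two, because no model is named yet to which a covariate could be added.

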Part 5 – Baby's health

- 42. For your "study pregnancy", what is your baby's sex at birth?
 - Male
 - Female
- 43. What was the baby's birth weight (lbs)?

Choose on a drop-down menu, including the following answers:

- Less than 1.5 kg / 3.4 pounds
- Between 1.5 and 2.49 kg / between 3 pounds 4 ounces and 5 pounds 8 ounces
- Weights with jumps of 100 gram up to 4 kg and the equivalent in pounds (2.5, 2.6, 2.7, 4)
- More than 4 kg / 8 pounds and 13 ounces

QMS document

TCH-011 Clinical Study Protocol

Doc ID: TECXXXX
Revision #: 1.0

Page: 24 of 25

44.	Was	the	baby	diagnosed	with	any	birth	defects?
-----	-----	-----	------	-----------	------	-----	-------	----------

- No
- Yes
- 45. Were there any complications with the baby after delivery?
 - No
 - Yes

If Yes, what type of complication?

- Neonatal jaundice,
- Newborn required admission to the neonatal intensive care unit
- Respiratory distress syndrome
- Infection such as sepsis
- Failure to thrive
- Low birth weight
- Other
- 46. Did your baby meet routine developmental milestones at 3 months? of life (such as smiling, gurgle, visually tracking objects, and rolling over within the first 3 months)
 - No
 - Yes
- 47. What was your baby's APGAR scores at 1 minute after birth?

We know it might be difficult to remember this score. Please check your discharge notes to find the 1 minute APGAR score, although not all notes include this information:

- Choose 1-10
- Don't know / Can't find the 5 min APGAR score

Use a dropdown menu, and add the option can't find

48. What was your baby's APGAR scores 5 minutes after birth? We know it might be difficult to remember this score. Please check your discharge notes to find the 5 minutes APGAR score, although not all notes include this information:

QMS document

TCH-011 Clinical Study Protocol

Doc ID: TECXXXX

Revision #: 1.0

Page: 25 of 25

- Choose 1-10
- Don't know / Can't find the 5 min APGAR score

Use a dropdown menu, and add the option can't find

- 49. Does the baby have any additional APGAR scores at 10, 15 or 20 minutes?
 - Yes
 - No
 - Don't know

If Yes, go to the next page, and ask for APGAR scores at 3 additional time points. Otherwise (answer: No or Don't know), go directly to the last page.

Page break

- 50. What was your baby's APGAR scores 10 minutes after birth? We know it might be difficult to remember this score. Please check your discharge notes to find the 5 minutes APGAR score:
 - Choose 1-10

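### Question 43 records birth weight in coarse classes below 2.5 kg and above 4 kg, and the plan has no coding rule, so the mean in secondary endpoint 1 is only approximate

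*Combined protocol and SAP*

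**What the plan says.** The secondary endpoints in the protocol's Endpoints section start with "Baby's birth weight (average birth weight". The endpoint is thus a group mean, and the stated aim is to show that the groups do not differ.

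Weight is collected in Appendix 2, Part 5, question 43, introduced by "Choose on a drop-down menu, including the following answers". The options are:

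- an open class, "Less than 1.5 kg / 3.4 pounds";
- one band, "Between 1.5 and 2.49 kg / between 3 pounds 4 ounces and 5 pounds 8 ounces";
- values in 100 g steps from 2.5 kg to 4 kg;
- an open class, "More than 4 kg / 8 pounds and 13 ounces".

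No numeric field and no don't-know option are listed. Question 45 has a "Low birth weight" box among the complications after delivery, but it records no weight.

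The Data analysis and Statistical Analysis Plan sections give no values for the coarse classes, no test for birth weight, and no assumed SD, margin or power for it. The sample-size figures there concern gestational age only.

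**The concern.** A mean needs a number for every baby. Here some babies have only a class, two of the three coarse classes are open-ended, and the value given to each is left to the analyst. The coding choice can change the estimated group difference, and without a rule it could be made after the data are seen.

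The coarse classes include the whole range below 2.5 kg, where detail matters in a fetal-safety study. Babies of 1.6 kg and 2.4 kg give the same answer. Because the study looks for no difference, a coding choice that shrinks a true difference would favour its intended conclusion.

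The two lowest classes also have inconsistent pound labels. The question asks for pounds, so respondents may well read those labels rather than the kilogram ones.

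**Working it through.** The plan states no figure for birth weight, so there is none to reproduce. The class limits below come from question 43. The distributions are assumptions: normal with mean 3.25 kg and SD 0.50 kg (case A), or mean 3.30 kg and SD 0.60 kg (case B).

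**1. Babies without a 100 g value.** Weights up to 4.05 kg are taken as rounded to the 4 kg step.

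- Below 2.5 kg, Φ((2.5 − mean)/SD). A: Φ(−1.50) = 6.7%. B: Φ(−1.33) = 9.1%.
- Above 4.05 kg, 1 − Φ((4.05 − mean)/SD). A: 1 − Φ(1.60) = 5.5%. B: 1 − Φ(1.25) = 10.6%.
- Total. A: 12.2%. B: 19.7%. With the cut at exactly 4.00 kg the totals are 13.4% and 21.3%.

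**2. How far the coarse classes leave a group mean undetermined.** Assume the open classes span 0.5–1.5 kg and 4–5 kg. The interval for the mean has width (share below 1.5) × 1.0 + (share 1.5–2.49) × 0.99 + (share above) × 1.0.

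- A: 0.0002 + 0.0666 × 0.99 + 0.0548 = 0.12 kg.
- B: 0.0013 + 0.0899 × 0.99 + 0.1056 = 0.20 kg.

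**3. Effect of the coding choice on a general shift.** The coded mean is the sum of (value × class probability). Midpoint coding uses 1.25, 2.0 and 4.25 kg for the coarse classes (the open-class values are assumed). Dropping averages the 100 g values only. Entries are differences in kg between a shifted and an unshifted group.

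| True shift | Midpoint, A | Midpoint, B | Dropped, A | Dropped, B |
|---|---|---|---|---|
| −0.10 | −0.106 | −0.102 | −0.057 | −0.044 |
| −0.20 | −0.214 | −0.205 | −0.113 | −0.088 |
| −0.30 | −0.323 | −0.309 | −0.167 | −0.131 |

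Midpoint coding slightly exaggerates the shift. Dropping keeps about 44–57% of it. The midpoint mean itself lies 0.02 kg (A) to 0.03 kg (B) below the true mean.

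**4. A shift confined to the 1.5–2.49 kg band.** Take a mixture with 97% of babies from mean 3.3 kg, SD 0.5 kg, and 3% from a low-weight component with mean 2.0 kg, SD 0.5 kg. Then 7.3% fall in the band. Making them up to 0.3 kg lighter, with a floor at 1.5 kg, moves the true mean by −0.021 kg (at most 0.073 × 0.3 = 0.022). The midpoint-coded mean does not move.

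**5. What the class counts still show.** For shifts of 0, −0.10, −0.20 and −0.30 kg, the share below 2.5 kg is 6.7%, 9.7%, 13.6% and 18.4% in case A, and 9.1%, 12.2%, 15.9% and 20.2% in case B. As a guide to sensitivity, a two-sided 5% comparison of 8% with 16% has 46% power at the planned 114 per group and 94% at the recruitment ceiling of 400.

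**6. Pound labels** (1 lb = 0.4536 kg).

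- The lowest class ends at 3.4 × 0.4536 = 1.54 kg.
- The next starts at 3 lb 4 oz = 3.25 × 0.4536 = 1.47 kg.
- The cut of 1.5 kg is 3.31 lb, or 3 lb 4.9 oz.

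Read literally, a baby between 3.25 and 3.40 lb, such as one of 3 lb 5 oz (3.31) or 3 lb 6 oz (3.38), fits both classes.

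**The case against.** Three stronger readings are tempting, and the documents support none of them.

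- *The mean cannot be computed.* It can be approximated. About 80–88% of babies have a 100 g value under the assumed distributions, and midpoint or interval-censored analysis uses the rest. What is missing is an exact value and a stated rule.
- *Growth restriction is hidden.* Counts below 1.5 kg and 2.5 kg survive, apart from the label overlap, and a general downward shift shows in them. Question 45 asks about low birth weight. Questions 20 and 42 give gestational age and sex, so weight can be read against both from 2.5 to 4 kg. Low weight is also not the same as growth restriction, since a preterm baby can be light but normal for age.
- *Any coding of the coarse classes pulls the groups together.* Under a general shift only dropping them does so, and nothing in the plan says that they will be dropped.

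It is also fair to say that birth weight is one of seven secondary endpoints, that study success rests on gestational age alone, and that the words introducing the drop-down may mean the listing is incomplete. The label overlap concerns far fewer than 1% of babies under the assumed normals, and the kilogram limits are clear.

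These points limit the severity. They do not supply a coding rule, and they do not restore the detail within the low classes, which no later analysis can recover.

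**Conclusion.** The concern holds in a limited form. Question 43 does not measure weight across the range that secondary endpoint 1 averages over, and the plan does not bridge the gap. About 12–20% of babies would have no 100 g value, leaving each group mean open by roughly 0.12–0.20 kg before a coding choice is made. That choice decides whether a general shift is recovered or roughly halved. A shift inside the 1.5–2.49 kg band is invisible to midpoint coding, although its effect on the mean is small (about 0.02 kg in the example).

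The percentages and shifts rest on assumed birth-weight distributions and, in part, on assumed values or limits for the open classes. The class structure, the missing rule and the label overlap are in the documents. This should be fixed, but it does not threaten the primary result.

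**What to change.** Before launch, replace the question 43 drop-down with numeric entry of pounds and ounces, or grams, with a range check and a don't-know option. Compute the mean, and the shares below 2.5 kg and 1.5 kg, from that value. This changes one survey field. Appendix 1 already advises participants to have their discharge documents at hand. The small downside is some typing errors, most of which the range check should catch.

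If the field cannot change, correct the pound labels so that the two lowest classes meet at one value. State in the analysis plan that question 43 will be analysed as interval-censored data including all classes, with the proportion below 2.5 kg reported alongside the mean. That costs a label correction and a short addition to the plan, but it does not recover severity within the low classes.

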- 6. Meeting developmental milestones following 3 months postnatal (% of babies)
- 7. Visits to the emergency room or urgent care due to pregnancy and/or migraine symptoms during pregnancy and 3 months postpartum period (# of events)

Exploratory endpoints: Difference between the study group and the control group in:

- 1. Overall subjective **feeling of safety** using acute migraine treatments during pregnancy (in subjects who used such treatments).
- 2. Overall subjective **satisfaction** with the acute migraine therapies used during the pregnancy (in subjects who used such treatments).
- 3. APGAR score at 5 minutes.

Data analysis

Statistical Hypothesis

The goal of the proposed study is to test the null hypothesis that treating with Nerivio during pregnancy does not impose a safety risk relative to standard care migraine treatment for pregnant women. In other words, the hypothesis is that the means of the two populations are equal. Thus, in this study, the following hypotheses will be tested:

• Null hypothesis: H0: GAt = GAc

• Alternate hypothesis: H1: GAt ≠ GAc

Where GAt and GAc are the average Gestational Age in the study group and control group, respectively. If the null hypothesis is not rejected, the study will be deemed successful. The criterion for significance has been set at 0.05. The test is 2-tailed.

TCH-011 Clinical Study Protocol

Doc ID: TECXXXX

Revision #: 1.0

Page: 7 of 25

Planned Sample Size

Based on USA data from 2020 [Osterman M, et al. Births: Final Data for 2020. Natl Vital Stat Rep. 2021] we assume mean gestational age (GA) of 38.4 with standard deviation of 2.7 (range 26-42).

With the proposed sample size of 114 for each group, the study will have power of 80% to yield a statistically significant result. This computation assumes that the mean difference is less than 1.0 week, and the common within-group standard deviation is 2.7. This effect was selected as the smallest effect that would be important to detect.

Precision for estimating the effect size: We further estimate the mean difference between the two populations. On average, a study of this design would enable us to report the mean difference with a precision (95% confidence level) of plus/minus 0.70 weeks.

Given this statistical requirement up to 400 participants will be recruited per group.

Statistical Analysis Plan

Data will be collected from all patients recruited to the study. Data analysis will not include patients who are:

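### No survey item records whether a live-born baby survived to three months, and the milestone endpoint has no stated denominator

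*Combined protocol and SAP*

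**What the plan says.** The Endpoints section sets the window: "Endpoints focus on the health of the mother and the baby, during pregnancy and three months postpartum". The Goal gives the same window for safety. Secondary endpoint 6 reads "Meeting developmental milestones following 3 months postnatal (% of babies"), with no statement of which babies are counted. Secondary endpoints 2 and 5 are miscarriage and stillbirth, so women whose pregnancy ended in a loss belong in the sample. No endpoint covers death after a live birth.

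The relevant items in Appendix 2 are:

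- **Q21** (Part 2) records pregnancy status: live birth, elective termination, "Spontaneous abortion (or miscarriage") or late fetal death.
- **Q26** (Part 2) asks whether baby and mother left hospital together, Yes or No.
- **Q45** (Part 5) asks "Were there any complications with the baby after delivery" and, if so, offers seven types, the last being Other with no text field shown.
- **Q46** (Part 5) asks "Did your baby meet routine developmental milestones at" 3 months, with answers No and Yes only.

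The Statistical Analysis Plan excludes women on BMI, LMP date and Nerivio use. It does not limit endpoint 6 to live births or survivors.

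**The concern.** Death is the most serious thing that can happen to the baby within the window the study claims to cover, and the survey gives it nowhere to be recorded. The study could report no difference in baby health while a death in either group sits unseen among the No answers, or the blanks, on a milestone question. There it would be indistinguishable from mild developmental delay.

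A second, smaller matter concerns the same item. Women with a miscarriage, termination or fetal death also answer this survey. Nothing written routes them past Q46 or gives them a not-applicable answer, and endpoint 6 does not say that they are left out. The milestone rate could therefore carry pregnancy losses that endpoints 2 and 5 already count.

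**Working it through.** **The plan's own figure.** The only sample size in the documents is for gestational age. Inputs from Statistical Hypothesis and Planned Sample Size: "The criterion for significance has been set at 0.05"; "The test is 2-tailed"; difference 1.0 week; SD 2.7; and "With the proposed sample size of 114 for each group, the study will have power of 80% to yield a statistically significant result".

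- n = 2 × (1.96 + 0.84)² × 2.7² / 1.0², which rounds up to 115 per group, against 114 stated.
- Power at 114 is 79.8%.
- Half-width of the 95% interval: 1.96 × 2.7 × √(2/114) = 0.70 weeks, as stated.

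The figure reproduces. It supplies the group sizes used below (114, and the recruitment ceiling of 400), but the point does not depend on it.

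**Step 1. Follow one case through the survey.** Take a baby born alive who dies at two weeks.

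| Item | Answer available | Does it identify the death? |
|---|---|---|
| Q21 | Live birth | No |
| Q26 | Yes or No | No; a No may be a longer stay |
| Q45 | Up to seven types, death not listed | No; Other has no text field |
| Q46 | No, Yes, or left blank | No; a No also means delay |

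No combination of these answers marks a death, so the information is absent from the dataset.

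**Step 2. How many deaths might be missed.** The documents give no rate, so the risk r by three months is an assumption. Expected deaths per group = r × N; chance of at least one = 1 − (1 − r)^N.

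| r | N = 114: expected; chance of ≥1 | N = 400: expected; chance of ≥1 |
|---|---|---|
| 0.2% | 0.23; 20% | 0.8; 55% |
| 0.5% | 0.57; 44% | 2.0; 87% |
| 1.0% | 1.14; 68% | 4.0; 98% |

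**Step 3. Is Part 5 tied to live birth?** Part 5 does contain branching: Q45 opens a list of complication types and Q49 leads to further APGAR scores. Neither depends on Q21. Not-applicable answers are written for Q22, Q36 and Q38, but not for Q42 to Q46.

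**Step 4. Worst-case effect on endpoint 6.** Let m be the true attainment among live births and L the share of pregnancies ending in loss, both assumed. If every woman with a loss answers No and nobody filters on Q21, the observed rate is m × (1 − L), a fall of m × L.

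| L | Observed rate, m = 95% | Fall (points) |
|---|---|---|
| 2% | 93.1% | 1.9 |
| 5% | 90.25% | 4.75 |
| 10% | 85.5% | 9.5 |
| 15% | 80.75% | 14.25 |

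For m from 90% to 98%, the fall runs from 1.8 points (0.90 × 2%) to 14.7 points (0.98 × 15%).

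**Step 5. Between groups, same worst case.** With m = 95% in both groups and loss shares of 5% and 10%, the rates are 90.25% and 85.5%, a spurious difference of 4.75 points. The chance that a two-sided 0.05 comparison of proportions is significant is Φ((0.0475 − 1.96 × SE₀)/SE₁), where SE₀ = √(2 × 0.87875 × 0.12125/N) and SE₁ = √((0.9025 × 0.0975 + 0.855 × 0.145)/N). This gives about 19% at N = 114 and 54% at N = 400.

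**The case against.** The strongest reply is on the milestone part. Q21 is asked of every respondent, so restricting Q46 to live births is a simple filter, and endpoint 6 already speaks of babies rather than pregnancies. For the rate to be distorted, women with losses must answer No rather than leave the item blank, and the analyst must ignore Q21. A spurious group difference also needs unequal loss shares, which endpoints 2 and 5 would themselves show. Eligibility requires at least four attacks in the pregnancy, and at least three treatments in the study group, which tends to remove the earliest losses. All of this stands. What remains is a denominator that should be written down.

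A reader might infer that Part 5 is put to every woman and that the milestone rate will therefore mix losses, deaths and delay. The documents do not support that. They show only that no rule is written. They do not say the items are mandatory, and the built e-survey may hold logic that the appendix omits.

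On infant death, the reply is that it is not a listed endpoint, that few are expected, and that Q26 and Q45 capture some serious neonatal illness. The small numbers mean that deaths can be described but not usefully compared. None of this makes a death identifiable, and unlike the milestone issue it cannot be repaired in analysis.

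**Conclusion.** The point holds in two parts of unequal weight.

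The main part rests on the text alone: the endpoints run to three months postpartum, and no item identifies a death after live birth. The expected number is small, from about 0.2 per group (r = 0.2%, N = 114) to 4.0 (r = 1.0%, N = 400), under risks that are assumptions.

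The lesser part is an undefined denominator for endpoint 6. The fall of about 2 to 14 points is a worst case that rests on assumed loss shares of 2% to 15%, an assumed attainment of 95%, every woman with a loss answering No, and no filter on Q21. It is not a prediction.

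Neither part touches the gestational-age endpoint or its sample size. The change is worth making because it is cheap and affects what a safety study can claim about the baby.

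**What to change.** - **Survival.** Add one item after Q45 for live births: was the baby alive at three months and, if not, the age at death. Report deaths after live birth to three months by group, descriptively, beside endpoint 5.
- **Milestones.** Show Q46 only for live-born babies alive at three months, and state in the Statistical Analysis Plan that they are the denominator of endpoint 6.
- **Rest of Part 5.** Show Q45 and the APGAR items only after a live birth at Q21. Keep Q42 to Q44 (sex, birth weight, birth defects) for late fetal deaths and terminations, with unknown and not-applicable answers. Limiting those three to live births would discard birth weight and sex for late fetal deaths, and birth weight is secondary endpoint 1.
- **Related items.** Q24, Q26 and Q41 also presuppose a delivery or a living baby; a not-applicable answer there would complete the repair.

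The cost is one sensitive question, a little skip logic and a short addition to the analysis plan. The sample size does not change.
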